**UCSD Human Research Protections Program**  
**RCHSD Only--New Biomedical Application**  
**RESEARCH PLAN INSTRUCTIONS**

Instructions for completing the Research Plan are available on the [HRPP website](#).  
The headings on this set of instructions correspond to the headings of the Research Plan.

General Instructions: Enter a response for all topic headings.

Enter "Not Applicable" rather than leaving an item blank if the item does not apply to this project.

**1. PROJECT TITLE**

Validation of ApneaLink Air home sleep testing in the diagnosis of Obstructive Sleep Apnea in Adolescent Children

**3. FACILITIES**

Rady Children's Hospital – Sleep Laboratory

**4. ESTIMATED DURATION OF THE STUDY**

1 year

**5. LAY LANGUAGE SUMMARY OR SYNOPSIS (no more than one paragraph)**

Obstructive sleep apnea (OSA) is highly prevalent in children affecting 2-3% of children and up to 10% of obese children. The reported prevalence is likely underestimated due to the lack of available laboratory polysomnography (PSG) testing for children. The high prevalence of OSA coupled with an increase in obesity, a major risk factor of OSA in children, has resulted in a significant strain for in laboratory PSG including children in the greater San Diego county. Currently, home sleep testing (HST) in children is restricted based on the limited availability of HST devices on children that have attained clearance by the US Food and Drug Administration (FDA). In this study, we will assess the feasibility and the validity of the ApneaLink Air HST device in children over the age of 12. The ApneaLink Air HST device is cleared for the diagnosis of OSA in adults and is frequently used amongst adult sleep medicine physicians. We will recruit twenty children over the age of 12 who will have their clinically indicated in laboratory PSG performed at Rady Children's Hospital. We will concurrent to their in-laboratory PSG have their sleep assessed using the ApneaLink Air device. Ten children will repeat the ApneaLink Air HST at home following their sleep study within one week, and the remaining ten children will in fact have their ApneaLink Air HST performed within one week prior to their in laboratory clinically indicated PSG.

**6. SPECIFIC AIMS**

1. To determine validity, feasibility, and accuracy of HST as a diagnostic tool for assessing children over the age of 12 for diagnosing OSA in children with symptoms compatible with OSA
2. To assess patient satisfaction with HST compared to in laboratory PSG in the diagnostic work up for pediatric OSA.

**7. BACKGROUND AND SIGNIFICANCE**

Obstructive sleep apnea (OSA) is a serious, common, and under diagnosed disorder that challenges healthcare resources. The typical presenting feature of OSA in children is snoring. The prevalence of snoring in children ranges from 3-12% but the exact prevalence of OSA in children using an overnight in laboratory PSG is about 2-3%. OSA is associated with numerous adverse health outcome issues such as behavioral, neurocognitive, and cardiovascular, metabolic complications as well as overall decreased quality of life. Behavioral issues include depression, behavior problems, aggression, excessive daytime sleepiness, and anxiety. Neurocognitive issues include decreased IQ, poor school performance, decreased executive function, learning difficulties, decreased information processing, decreased memory, poor visuo-spatial skills, language, verbal skills, and attention deficits. Cardiovascular complications range from endothelial dysfunction systemic hypertension to pulmonary hypertension secondary to recurrent hypoxia and hypercapnia leading to cor-pulmonale. Asymptomatic degrees of pulmonary hypertension have been reported in up to 40% of pediatric patients with OSA.

Comparing to the gold standard of in-laboratory PSG, other methods of diagnosing OSA including by history, physical examination, radiological studies, assessment of snoring and ambulatory PSG including home oximetry have reasonable specificity but limited sensitivity (high false negative rate). When in laboratory PSG is not available, clinicians are recommended to utilize these alternative approaches.

Notwithstanding, given the increased awareness of the complications related to Pediatric OSA more children are screened for OSA and undergo some form of diagnostic evaluation. While in-laboratory PSG remains the gold standard for diagnosing OSA in children, the dearth of Pediatric sleep labs and Pediatric sleep specialists has rendered it challenging to adequately diagnose children referred for symptoms suggestive of OSA. In addition to limited availability of in laboratory pediatric PSG which is also observed in the greater San Diego county, there is a high resource burden associated with obtaining an in laboratory PSG as it requires specialized personnel, equipment, laboratory space, and the need for a child and at least one caretaker to spend the night outside the comfort of their homes.

HST is considered as a valid alternative to adults with OSA symptoms as it is more cost effective, convenient, and accessible. As a result HST has become the standard of care in adult sleep medicine HST devices vary in the number of parameters that are typically recorded and hence there is variation in the sensitivity and specificity of HST devices when compared to the gold standard in diagnosing adult OSA.

Applicability of HST in children is rather limited as many children are intolerant to specific devices including the nasal cannula resulting in data collection that is lower quality or unacceptable altogether. Certainly, this limited tolerance is anticipated more often in younger children. Despite this preliminary studies have been encouraging. Brockman et al demonstrated a 93% success rate of HST conducted in children with an average age of 2.8 years of age and found no difference in success rates between in laboratory PSG and HST. A recent systematic review corroborated the above conclusions and revealed a sensitivity of 76%, a specificity of 77%, and an area under the curve of 0.88 which attested to the fact that unattended HST perform well for predicting pediatric OSA. However, further studies enabling head-to-head comparisons and validation of specific clinical algorithms are needed. The inability to determine total sleep time absence of EEG testing and subsequent inability to score respiratory events that culminate in arousal as opposed to desaturation and finally inability to identify sleep architecture can culminate the utility of HST particularly in young children. While these issues may be more problematic in young children, HST may be more useful in adolescents with OSA as OSA during adolescence parallels what is observed in adults

## **8. PROGRESS REPORT**

N/A

## **9. RESEARCH DESIGN AND METHODS**

### Target Population:

Twenty nonsyndromic children over the age of 12 who will be undergoing a clinically indicated in laboratory PSG to rule out OSA will be approached for recruitment. In laboratory PSG testing is performed at Rady Children's hospital. In addition to children with syndromes or congenital disease, children with craniofacial abnormalities, congenital heart disease, and pulmonary hypertension will be excluded. Demographic data including age, race, sex, and obesity status will be collected.

### Experimental procedure:

Of the twenty children recruited, ten will undergo home sleep testing (HST) no greater than one week prior to their in-laboratory PSG, while the other ten children will undergo HST no greater than one week following their in laboratory PSG. Participants who are randomized to receive the HST prior to their in-laboratory PSG will have the Resmed ApneaLink Air mailed to their home address. This will avoid the additional need for a study visit. All twenty children will also undergo their HST concurrent to their in-laboratory PSG. The rational for splitting children in these two groups is to equally distribute the effects of the first night evenly, in which

the sleep architecture including reduced total REM sleep time can vary in some children during their first ever sleep study. As the HST will be compared to the in-lab PSG, we would like to evenly distribute this effect by having two groups of ten children.

Upon obtaining consent by the PI, [name], or the research coordinator, [name], the subject will be provided with a verbal explanation and instructions on how to use the device. These instructions (both Spanish and English version) will also be included with the device they will take home at the time of their sleep lab appointment. Information about how to apply the ApneaLink Air device at home will be demonstrated by sleep technologists who are members of the research team. A hotline number will be provided to the patients and parents in order to answer questions or problem solve.

For home sleep testing (HST), the participants will use the Resmed ApneaLink Air™ device (Resmed, San Diego, USA). The ApneaLink Air is a device used to assess for sleep-disordered breathing. ApneaLink Air records five channels of information: respiratory effort, pulse and pulse oxygen saturation, nasal flow, body position and snoring. It includes a chest belt, nasal cannula, oximeter and recording device. This device is approved by the FDA for use in diagnosing OSA in adults. This device is not yet approved for use in the proposed subject population (12-17 years old) and the data obtained from this study may be used for the application of an FDA approval for children over 12. No clinical interventions will be implemented based on the results of the home sleep test.

This device is a non-significant risk device as it poses minimal risk or clinical harm to the pediatric population. The following criteria for a device to be deemed non-significant risk are met:

1. The device is NOT intended as an implant that presents a potential for serious risk to health, safety, or welfare of a subject
2. The device is NOT purported or represented to be for a use in supporting or sustaining human life that presents a potential for serious risk to the health, safety, or welfare of a subject
3. The device is NOT for a use of substantial importance in diagnosing, curing, mitigating, or treating disease, or otherwise preventing impairment of human health that presents a potential for serious risk to the health, safety, or welfare of a subject
4. The device does NOT otherwise present a potential for serious risk to the health, safety, welfare of a subject.

Furthermore, adolescents with suspected OSA (the study population) tend to parallel the OSA presentation of adults. Thus, no additional risk, other than those for adults, will incur to the patient if the device is used by the study population.

As stated, all subjects will have ApneaLink Air performed twice, once at home, and once during the sleep study. All of the components of the ApneaLink Air device will be placed in addition to the equipment used in the sleep lab. With exception to the nasal cannula, this should not interfere or result in additional discomfort to the in-lab sleep study. With regards to the nasal cannula, a 'splitter' will be used in which one nasal cannula will provide information on flow to both the ApneaLink Air device as well as the in-laboratory lab equipment (Nihon Koden, Irvine CA)

For ApneaLink Air testing performed at home, these subjects will receive a shipping box and return label to return the device following completion.

All children undergoing sleep study testing will have routine clinical surveys be performed. Some of this information will be gathered for research purposes to assess the pre-test probability of OSA. Following the home sleep test and in lab sleep test, all children will be interviewed by the research coordinator and asked questions concerning the child's experiences and comparing the two environments for their sleep test via a

telephone follow-up.

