#### Data Analysis:

Descriptive statistics will be used to summarize the children's demographic and polysomnographic characteristics. Comparisons between in laboratory sleep study and HST will be conducted using Mann Whitney U-Test for not-normal data, and Student's t-test for normally distributed variables. Factors that may have influenced the interpretability of the recordings will be investigated using logistic regression. Age, gender, AHI, and BMI z- scores will be analyzed as independent variables in the logistic regression equation. Odds ratios and their 95% confidence intervals (95% CI) will be calculated. A p-value <0.05 will be considered statistically significant. Any information that will be sent to the sponsor will be de-identified.

The criteria for an unfeasible HST or HST failure will be defined as:

1. Loss of the nasal flow channel, or thoracic or abdominal sensor
2. Recordings with less than 4h of artifact-free recording time
3. Less than 4h of SpO2 signal

All studies will be scored by a trained sleep technician, and interpreted by [name], in order to avoid variability. Both sleep scoring and sleep interpretations will be blinded from the findings of HST performed at home and in the sleep lab.

In the event that the HST is deemed not valid or inadequate when compared to the in laboratory PSG, the subject will remain in the study and will use this data to evaluate validity and feasibility of HST. Information

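### The order of home test and lab study is randomised to balance the first-night effect, but the planned home-versus-lab analysis does not use that order

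*Combined protocol and SAP*

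**What the plan says.** The sample is "Twenty nonsyndromic children over the age of 12 who will be undergoing a clinically indicated in laboratory PSG" (section 9, Target Population). Under Experimental procedure the order is split evenly: "Of the twenty children recruited, ten will undergo home sleep testing (HST) no greater than one week prior to their in-laboratory PSG", and the other ten within a week after it. The split is called random in one sentence, with no method given: "Participants who are randomized to receive the HST prior to their in-laboratory PSG will have the Resmed ApneaLink Air mailed to their home address".

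The only stated purpose is this: "The rational for splitting children in these two groups is to equally distribute the effects of the first night evenly". The same paragraph ties that purpose to the comparison of HST with in-lab PSG. There is also a same-night comparison: "All twenty children will also undergo their HST concurrent to their in-laboratory PSG".

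Under Data Analysis the plan reads "Comparisons between in laboratory sleep study and HST will be conducted using Mann Whitney U-Test", with Student's t-test for normally distributed variables. The only model is a logistic regression for whether recordings can be interpreted: "Age, gender, AHI, and BMI z- scores will be analyzed as independent variables in the logistic regression equation". No order term, stratification by order or summary by order appears. The available text of that section stops mid-sentence, but nothing in what can be read uses order.

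**The concern.** The authors treat the first night as a threat to the home-versus-lab comparison and build the design around it. The analysis then drops the one variable that carries the protection.

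Two things follow. First, a first-night effect pushes the within-child home-minus-lab difference one way when home comes first and the other way when the lab comes first. If order is ignored, that spread is counted as noise. In a 20-child study judged by p < 0.05, extra noise makes a real home-lab difference harder to detect, and a non-significant result is easily misread as agreement. Aim 1 (section 6) is validity and accuracy, and section 9 says the data may support an FDA application.

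Second, the effect cancels from the mean only while the two orders supply equal numbers of usable home recordings. The shift would be systematic only if failure depends on order. That is plausible, because one group receives the device by mail and the other has already worn it in the lab, but the documents do not show it.

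**Working it through.** **Inputs from the documents.** There are 20 children, 10 per order, and significance is set at p < 0.05. No precision target, SD, first-night effect or failure rate is given, so there is no stated figure to reproduce. The values of L and the usable numbers below are assumptions, shown as a range.

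**Model.** Let L be the shift on a child's first study night, the same at home and in the lab. Let s be the within-order SD of the home-minus-lab difference, set to 1. The expected difference is:

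- home first (n1 children): bias + L
- lab first (n2 children): bias − L

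**Formulas**, with n = n1 + n2:

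- Expected variance of the pooled differences = s² + 4L²·n1·n2/[n(n−1)]. At 10/10 this is s² + 20L²/19.
- Pooled 95% half-width = t(0.975, n−1)·√(variance/n).
- Order-adjusted half-width = t(0.975, n−2)·(s/2)·√(1/n1 + 1/n2).
- Shift of the pooled mean = L(n1 − n2)/n.

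**Width.** At 10/10 and L = 0.5 the variance is 1 + 20(0.25)/19 = 1.263.

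| Usable | L (in SD) | Pooled | Adjusted | Pooled/adjusted |
|---|---|---|---|---|
| 10/10 | 0 | 0.468 | 0.470 | 0.996 |
| 10/10 | 0.25 | 0.483 | 0.470 | 1.03 |
| 10/10 | 0.5 | 0.526 | 0.470 | 1.12 |
| 10/10 | 1.0 | 0.671 | 0.470 | 1.43 |
| 10 vs 7 | 0 | 0.514 | 0.525 | 0.98 |
| 10 vs 7 | 0.5 | 0.577 | 0.525 | 1.10 |

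**Coverage** (simulation, 200,000 draws, 10/10). The pooled interval covers 95.0%, 97.1% and 99.4% at L = 0, 0.5 and 1. The adjusted interval covers 95.0% to 95.1% throughout. The pooled interval is therefore too wide, not too narrow.

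**Shift of the mean** (absolute size):

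- 10 vs 9: 1/19 = 0.053L
- 10 vs 8: 2/18 = 0.111L
- 10 vs 7: 3/17 = 0.176L

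At 10 vs 7 and L = 0.5 SD the shift is 0.176 × 0.5 = 0.09 SD, against an adjusted half-width of 0.53 SD.

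**Power** (simulation, 4,000 runs per setting, 10/10). The assumptions are a true home-lab difference of 0.5 single-night SD and a within-child correlation of 0.7. As the night effect rises from 0 to 0.6 single-night SD, power changes as follows:

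- paired test without order: 0.79 to 0.60
- paired with order: 0.78 at both ends
- unpaired t-test: 0.25 to 0.21

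**Unequal effects.** If the first-night shift is Lh at home and Ll in the lab, the equal-weighted mean of the two order groups is bias + (Lh − Ll)/2. For example, Lh = 0.25 and Ll = 0.5 leave −0.125.

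**The case against.** The strongest reply is that the 10/10 split already does what the protocol promises. A constant first-night effect cancels from the mean without a model term, and the unadjusted paired interval errs on the cautious side. This is right, so the loss at 10/10 is one of precision and does not bias the result.

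A second reply is that the figures do not describe the plan as written, which names tests for independent groups and never mentions pairing. That also stands. The power figures show that pairing matters more than order (0.25 against 0.79 with no night effect), and an order term makes sense only on within-child differences. It limits the numbers but does not justify leaving order out, because the fix specifies those differences.

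Third, L is unknown. At 0.25 SD the gain is only 3%, and an effect that varies between children, which the protocol's reference to some children suggests, would be only partly removed. That is fair, and the larger figures are conditional on a large constant effect.

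Fourth, unequal usable numbers are not inevitable. Children whose HST is inadequate stay in the study, and the plan offers instructions, a hotline and a demonstration: "Information about how to apply the ApneaLink Air device at home will be demonstrated by sleep technologists who are members of the research team". These may reduce failures. A child can stay in the study and still have no usable home value, so imbalance remains possible.

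Finally, Data Analysis does not say whether HST there means the home or the concurrent recording. If only the concurrent one were meant, order would not matter, but the split would then serve no comparison.

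**Conclusion.** The concern holds. The protocol randomises order for one stated reason, and no available analysis text uses it.

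With 10/10 usable recordings the cost is precision: nothing if L = 0, rising to a 12% wider interval at L = 0.5 SD and 43% at L = 1 SD. With unequal usable numbers the mean also shifts, by 5% to 18% of L for 9 down to 7 usable against 10, which is small beside the interval width. These sizes rest on assumed L, assumed failures, a constant first-night effect equal in both settings, and a within-child analysis.

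The point applies only to home HST versus in-lab PSG. The change should be made because it is nearly free, but the omission alone does not invalidate the study.

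**What to change.** Add wording to this effect under Data Analysis:

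> Home HST will be compared with in-lab PSG using within-child differences, with randomised order as a factor. The estimate is the equal-weighted mean of the two order-specific mean differences, with its 95% confidence interval. The differences and the home HST failure rates will also be reported by order.

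State alongside it that this removes the first-night effect fully only if the effect is the same size at home and in the lab; otherwise (Lh − Ll)/2 remains. With ten children per order, the by-order results should be read as descriptive. The concurrent HST-versus-PSG analysis needs no order term.

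The cost is this wording and one degree of freedom. If there is no first-night effect, the interval is 0.4% wider at 10/10 (0.470 against 0.468) and 2% wider at 10 vs 7 (0.525 against 0.514). No extra visits or measurements are needed, since order follows from the assignment. The change does require the comparison to be made within child.

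### The 10/10 split balances recording order but not any lab-versus-home shift, and the analysis does not use the concurrent device recording that could separate that shift from device error

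*Combined protocol and SAP*

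**What the plan says.** Section 9, Experimental procedure, divides the twenty children into two groups. In one, "ten will undergo home sleep testing (HST) no greater than one week prior to their in-laboratory PSG"; the others have the home test within a week after the PSG. Allocation is described as randomized, with no method given. The reason for the split is "The rational for splitting children in these two groups is to equally distribute the effects of the first night evenly", and the effect in view is that "reduced total REM sleep time can vary in some children during their first ever sleep study". The same section adds: "All twenty children will also undergo their HST concurrent to their in-laboratory PSG". Each child therefore contributes three measurements over two nights: a home HST, a lab HST and a PSG, the last two on the same night through a shared nasal cannula with a splitter.

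Section 9, Data Analysis, gives the comparison as: "Comparisons between in laboratory sleep study and HST will be conducted using Mann Whitney U-Test for not-normal data", with Student's t-test for normally distributed variables. It names no pairing, no sequence or location term, and no contrast between a child's two HST recordings.

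**The concern.** Counterbalancing removes an effect that changes sign with order. A difference between a night in the lab and a night at home does not change sign: it falls on the PSG in all twenty children and on the home HST in none. A gap between home HST and PSG could therefore come from the device, from the setting, or from ordinary change between nights. The home recording cannot settle the matter alone, since Section 7 notes that HST has no EEG and cannot show sleep architecture.

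Aim 1 concerns validity and accuracy, and the plan says the data may support an FDA application. If home HST versus PSG were read as device error, an accurate device could look biased, or a biased device could look accurate. If the choice of HST recording were left until the data are in, either account could be given.

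**Working it through.** **Inputs from the documents.** Twenty children, 10 home-first and 10 lab-first; one PSG each, in the lab; two HST recordings each, one at home and one during the PSG. The plan states no effect size, SD or agreement limit, so there is no figure of its own to reproduce.

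**Model.** Measurement = child mean + d (if HST) + L (if in the lab) + f (if first recorded night), with no interactions.

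| Contrast | Home-first | Lab-first | 10:10 mean |
|---|---|---|---|
| Home HST − PSG | d − L + f | d − L − f | d − L |
| Concurrent HST − PSG | d | d | d |
| Home HST − concurrent HST | −L + f | −L − f | −L |

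The order effect f averages out, so the split does its stated job; with all children lab-first the mean would be d − L − f. L remains in both groups.

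**Estimability.** The design matrix for (mean, d, L, f) has rank 4 of 4 with the concurrent HST and rank 3 of 4 without it. Only the concurrent recording separates d from L.

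**Illustrations of the mean (assumed values, events/h).**
- d = 0, L = 2: home HST − PSG = 0 − 2 = −2 in both groups, so an accurate device looks biased.
- d = 0, L = −2: 0 − (−2) = +2.
- d = 2, L = 2: 2 − 2 = 0, so a real bias is hidden. Concurrent HST − PSG still shows 2.

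**Illustration of spread (assumed device SD 2, f = 1, night-to-night SD s = 2, 3, 4).** The 95% limits of agreement for home HST − PSG have half-width 1.96·√(2² + 2s² + 1²) = 1.96·√(5 + 2s²), which is 7.1, 9.4 and 11.9. For concurrent HST − PSG it is 1.96 × 2 = 3.9. L does not enter these widths; the difference reflects mainly night-to-night variation and would be there if L were 0.

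**What balancing f leaves behind.** It protects the mean only. The f² term inflates the SD of home HST − PSG differences by √(1 + 0.5²) = 1.12 if f is half the remaining SD, and by √2 = 1.41 if f equals it. Failed recordings can also upset the balance: with 6 home-first and 10 lab-first usable pairs (an assumption), the raw mean keeps f × (6 − 10)/16 = −0.25f.

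**Precision.** At n = 20 the 95% CI half-width of a paired mean difference is 2.093/√20 = 0.47 SD of the differences (0.53 SD with an assumed 16 pairs). With the SDs above, independent device errors on the two nights, and f removed by the sequence factor, the SD of home HST − concurrent HST is √(2s² + 8) = 4.0, 5.1 and 6.3. The half-width is then about 1.9, 2.4 and 3.0 events/h.

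**The case against.** A reader might infer that the split fails at its stated purpose. The documents do not support that. The plan describes an effect of the first sleep study, which is an order effect, and the split balances it on average. The plan makes no claim about lab location.

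A reader might also infer that AHI is known to shift in the lab, or that the study cannot tell such a shift from device error. Neither is supported. No passage gives a lab-versus-home shift in AHI, so L could be zero. The concurrent recording in all twenty children is what is needed to separate the two.

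Nor does Data Analysis confine itself to home HST versus PSG. It speaks of comparisons in the plural, and its blinding sentence mentions both home and lab HST. The text is ambiguous rather than wrong.

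These points stand and narrow the concern to the analysis. They do not remove it: having a recording is not the same as planning to use it. The named tests also ignore the pairing. Mann-Whitney is for independent samples, and the t-test set beside it is not described as paired.

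**Conclusion.** The concern holds for the analysis text, not as a fault in the allocation. Home HST versus PSG estimates d − L whatever the order. The plan collects what is needed to separate the two but does not specify the analysis that would do so.

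The size of the problem is unknown, because it equals L and the documents give no value; every figure in events/h above is illustrative. That L does not cancel needs no value for L. Recovering L does assume no order-by-location interaction. If the first-night effect is f_H at home and f_L in the lab, home HST − PSG averages d − L + (f_H − f_L)/2. Concurrent HST − PSG remains d in either case. No eligibility rule excludes an earlier sleep study, so the first recorded night need not be a child's first ever.

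One further inference should be resisted: that concurrent HST versus PSG captures all device error. It is measured in an attended lab with a shared cannula, so it cannot show errors specific to unattended home use. Home HST versus concurrent HST correspondingly mixes night, setting and self-application, and twenty children estimate it only roughly.

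**What to change.** In Section 9, Data Analysis, replace the general comparison with three pre-specified paired contrasts:

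1. **Concurrent HST versus same-night PSG:** device agreement under attended lab conditions, with the shared cannula noted.
2. **Home HST versus concurrent HST:** the combined night, setting and self-application difference.
3. **Home HST versus PSG:** total performance in practice.

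For each, report the mean within-child difference with its 95% CI and the limits of agreement. In (2) and (3), include sequence (home-first or lab-first) as a factor, coded so that the intercept weights the two groups equally; this keeps f out of the mean when failures leave unequal groups. State that (3) alone will not be read as device error and that (1) does not cover errors specific to unattended home use.

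Experimental procedure needs at most a clause saying that the split addresses recording order only.

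The cost is a paragraph of text and one extra contrast. All the recordings are already planned in all twenty children, so there are no added visits or burden.
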